10.4 Analyses Addressing Protocol Objectives

10.4.1 Analyses of Primary Objectives

10.4.1.1 Immunogenicity

The Per-Protocol (PP) population (ie, randomized subjects who received the assigned dose of the test article according to the protocol, have HAI serology results at Day 0 and Day 28, and have no major protocol deviations) will be the primary population for immunogenicity analysis. A separate intent-to-treat (ITT) population analysis will not be produced unless > 5% of at least

Nanoparticle Influenza	Vaccine, Quadrivalent	Confidential	qNIV-E-301 Protocol
Novavax, Inc.	Version 4	4.0 – 31 October 2019	Page 60

1 treatment group is excluded from the PP population. No missing data will be imputed. For GMTs and GMRs, titers reported below the lower limit of quantitation (LLOQ, ie, below the starting dilution of assay reported as "< 10") will be set to half that limit (ie, 10/2 = 5).

For purposes of determining non-inferiority (and exploratory superiority) in immunogenicity of 240 μ g Quad-NIV co-formulated with 75 μ g Matrix-M1 adjuvant, relative to a US-licensed comparator, Fluzone Quadrivalent, for all Quad-NIV homologous influenza strains (2 influenza A and 2 influenza B strains) at 28 days post-vaccination, derived/calculated endpoints will include:

- Two-sided 95% CIs for the ratio of Day 28 post-vaccination GMTs between Quad-NIV and Fluzone Quadrivalent will be constructed using log normal distribution. The log₁₀ values will be used to construct a CI using the analysis of covariance (ANCOVA) with treatment group and baseline at Day 0 (adjusted for intergroup variation in baseline [pre-vaccination] titers) as the covariates under two-sided type I error rate of 0.05. No type I error rate adjustments will be made. The mean difference and the corresponding CI limits will then be exponentiated to obtain the ratio of GMT and the corresponding CI.
- Two-sided 95% CIs for the difference of the SCRs between Quad-NIV and Fluzone Quadrivalent will be based on the Newcombe hybrid score (METHOD = SCORE riskdiff-option for PROC FREQ in SAS).

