Subject randomization will be conducted using an Interactive Web Randomization System (IWRS). Stratification will be by site, age, and history of receipt of the 2018-19 influenza vaccine. Proportions of subjects in the various strata will not be pre-specified; rather, the goal will be to achieve an approximately equal distribution of subjects with these characteristics across the two treatment groups.

Preparation and administration of each test article dose will be performed by unblinded vaccine pharmacists/administrators. These persons, identified prior to trial dosing, will not perform any trial assessments post-dosing.

^[1] Fluzone Quadrivalent will be administered at the manufacturer's recommended dose and volume.

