3.4.1 Protocol Deviations

A protocol deviation (PD) will be defined as a failure to comply with the requirements set forth in the protocol. PDs may be determined programmatically through the course of the trial. Examples of programmatically-determined PDs are provided in Table 2.

Table 2: Programmatically-Determined Protocol Deviations

Missed Visit
Out of Window Visit
Trial Procedure Not Done
Randomization Error

The following rules will be applied to capture programmatically determined PDs.

- Missed Visit information in protocol deviations derived from the eCRF will be subordinate to those programmatically-determined missed visits and will not be used for the formal CSR. Missed Visit status will not be triggered by the "Subject Diary Review" procedure. Missed Visit applies to planned in-clinic visits at Days 0, 7, 28, and 182. Telephone contacts will not be counted as missed visits, though the presence or absence of these visits will be apparent in the data listings. If a subject withdraws from the study early, no subsequent protocol deviations will be checked.
- Out of Window Visit will be determined by comparing the actual visit day to the scheduled visit day. If a subject missed a particular visit (s), (s)he will not be considered as "Out of Window" for that visit but will be counted as "Missed Visit". Out of Window visit applies to all planned trial visits at Days 0, 3, 7, 28, 90, 182, and 364. Telephone contacts will not be reviewed for visit windows, however the date of occurrence will be present in the data listings.
- Trial Procedure Not Done will include trial procedures ("Physical Exam", "Vital Signs", "Serology", "PBMC for CMI" and "Trial Treatment Injection") listed in Appendix 1 "Trial Procedure Schedule" in the protocol. If a subject had "Missed Visit" or "Out of Window Visit", (s)he will not be counted as "Procedure Not Done" again for the intended visit.
- Randomization Error will be determined programmatically by seeking possible erroneous scenarios including mis-stratification based on erroneous age or 2018-19 influenza vaccine history, possible multiple randomization, randomization without treatment, or treatment without randomization.

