7 ANALYSES ADDRESSING PROTOCOL OBJECTIVES

7.1.1 Analyses of Primary Immunogenicity Objectives

The Per-Protocol (PP) population (ie, randomized subjects who received the assigned dose of the test article according to the protocol, have HAI serology results at Day 0 and Day 28, and have no major protocol deviations) will be the primary population for immunogenicity analysis. A separate intent-to-treat (ITT) population analysis will not be produced unless > 5% of at least 1 treatment group is excluded from the PP population. No missing data will be imputed. For

Version 3.0 - 01 November 2019

GMTs and GMRs, titers reported below the lower limit of quantitation (LLOQ, ie, below the starting dilution of assay reported as "< 10") will be set to half that limit (ie, 10/2 = 5).

For purposes of determining non-inferiority (and exploratory superiority) in immunogenicity of 240 µg Quad-NIV co-formulated with 75 µg Matrix-M1 adjuvant, relative to a US-licensed comparator, Fluzone Quadrivalent, for all Quad-NIV homologous influenza strains (2 influenza A and 2 influenza B strains) at 28 days post-vaccination, derived/calculated endpoints will include:

- Two-sided 95% CIs for the ratio of Day 28 post-vaccination GMTs between Quad-NIV and Fluzone Quadrivalent will be constructed using log normal distribution. The log₁₀ values will be used to construct a CI using the analysis of covariance (ANCOVA) with treatment group and baseline at Day 0 (adjusted for intergroup variation in baseline [pre-vaccination] titers) as the covariates under two-sided type I error rate of 0.05. No type I error rate adjustments will be made. The mean difference and the corresponding CI limits will then be exponentiated to obtain the ratio of GMT and the corresponding CI.
 - A sample SAS code for between-group geometric mean ratio (GMR_{new/ref}) is given below:

```
proc mixed data= fludata;
      by Visit;
      class Treatment;
      model log(HAI 28) = log(HAI D0) Treatment/noint;
      lsmeans Treatment/cl diff e alpha=0.05;
run;
```

- Two-sided 95% CIs for the difference of the SCRs between Quad-NIV and Fluzone Quadrivalent will be based on the Newcombe hybrid score (METHOD = SCORE riskdiff-option for PROC FREQ in SAS).

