 - Pearson Chi-Square p-value will be derived for testing the equality of SCRs between two groups; otherwise Chi-Square p-value will be derived with continuity adjustment if small sample size. The Newcombe method will be used to construct its 95% confidence interval with the following sample SAS code:

```
proc freq data = fludata noprint;
      tables trt*seroconvind / riskdiff (column=2 cl=(newcombe))
      chisq;
run;
```

7.2 **Analysis of Secondary and Exploratory Immunogenicity Objectives**

Immunogenicity of 240 µg Quad-NIV co-formulated with 75 µg Matrix-M1 adjuvant, relative to a US-licensed comparator, Fluzone Quadrivalent, based on HAIs (assayed with both egg-propagated virus and wild-type VLP reagents) for all vaccine-homologous influenza A and B strains, and at least 1 antigenically-drifted A or B strain at Day 28 post-vaccination, will be measured in terms of:

- Geometric mean titer (GMT) defined as the antilog of the mean of the log-transformed HAI titers, on Days 0 and 28.
- Geometric mean ratio (GMR) defined as the ratio of post-vaccination to pre-vaccination (Day 0) HAI GMTs (GMR_{Post/Pre}) on Day 28.
 - Within-group geometric mean ratio (GMR_{post/pre}) for each arm will be conducted using paired t distribution. A sample SAS code is given below:

```
proc ttest data= fludata alpha=0.05;
      by Treatment Visit;
      PAIRED log(HAI D28) *log(HAI D0);
run;
```

- Seroconversion rate (SCR) defined as proportion of subjects in a given treatment group with either a baseline reciprocal (Day 0) titer of < 10 and a post-vaccination reciprocal titer \geq 40, or a baseline reciprocal (Day 0) titer of \geq 10 and a post-vaccination titer \geq 4-fold higher on Day 28.
 - SCR and corresponding 2-sided exact binomial 95% CIs will be calculated using the Clopper-Pearson method with the following sample SAS code:

```
proc freq data=fludata noprint;
      by Treatment;
      tables seroconvind / binomial(exact) alpha=.05;
      output out=out1 binomial;
run;
```

- Seroprotection rate (SPR) defined as the proportion of subjects with a reciprocal HAI titer \geq 40 on Day 28.
 - SPR and corresponding 2-sided exact binomial 95% CIs will be constructed similarly using the Clopper-Pearson method. Chi-Square p-value will be derived for testing the equality of SPRs between two groups similarly as SCR described above. The Newcombe method will be used to construct its 95% confidence interval.

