9 SAMPLE SIZE CONSIDERATIONS

This study has a single comparison between Quad-NIV and Fluzone Quadrivalent at Day 28 post-vaccination for the primary immunogenicity objective. No adjustment of the Type I error rate for multiple comparisons is warranted since the simultaneous successes of all 8 comparisons planned for the 4 strains contained in the vaccines and the two endpoints (GMT and SCR) are required for the demonstration of the primary non-inferiority objective of the study.

Non-inferiority is defined as the lower bound of the 2-sided 95% CI on the ratio of GMTs (Quad-NIV vs Fluzone) ≥ 0.67 (ie, unadjusted 1-sided p-value < 0.025 against the null hypothesis of H0: Ratio of GMT < 0.67) and the lower bound of the two-sided 95% CI on the

difference of the SCRs (Quad-NIV - Fluzone) \geq -10% (ie, unadjusted 1-sided p-value < 0.025 against the null hypothesis of H0: Difference of SCRs < -10%).

For the calculation of sample size estimation, we used assumptions of true differences, ie, the ratio of GMTs (Quad-NIV vs Fluzone Quadrivalent) is 1.0 for all 4 homologous strains, and the difference of the SCRs is -2% for each of the 4 homologous strains, based on the average performance in the previous trial (qNIV-E-201). To achieve an overall 90% power (ie, ~ 97.5% power for each of the 4 strains) to demonstrate a non-inferiority margin for SCR difference of -10%, the SCR of reference group (Fluzone Quadrivalent) is assumed to be 0.5 and the SCR of treatment group (Quad-NIV) is assumed to be 0.48 under the null hypothesis of inferiority (H0: Difference of SCRs < -10%). The significance level of the testing is 0.025. Sample size was estimated to be 1195 in each group by assuming equal size in each group. The sample size accounted for a 10% attrition rate for the per-protocol population such that the primary analysis population for all immunogenicity endpoints will be 1325 in each group.

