12.2 Adjustments for Covariates

Comparison of GMTs between treatment groups will be adjusted for pre-vaccination titer.

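### The strata used to randomise (site, age group, 2018-19 vaccination) enter neither primary analysis, so the SCR interval may be slightly conservative and a small gain in power is forgone

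*SAP*

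**What the plan says.** SAP 1.2 and protocol 3.3 describe randomisation through the IWRS: "Stratification will be by site, age, and history of receipt of the 2018-19 influenza vaccine". The age groups are below 75 and 75 or older. Stratum sizes are left open ("Proportions of subjects in the various strata will not be pre-specified"), and the stated aim is balance between the two arms.

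The primary analyses are in SAP 7.1.1 and protocol 10.4.1.1.

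- **SCR difference.** The protocol says the interval for Quad-NIV minus Fluzone "Quadrivalent will be based on the Newcombe hybrid score". The SAP code is "tables trt*seroconvind / riskdiff (column=2 cl=(newcombe", a single treatment-by-seroconversion table with no stratum variable.
- **GMT ratio.** An "analysis of covariance (ANCOVA) with treatment group and baseline at Day 0" as its only terms. SAP 12.2 confirms this: "Comparison of GMTs between treatment groups will be adjusted for pre-vaccination titer". It names no other covariate and says nothing about SCR.

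Outside the design description, the factors reappear in the SAP only in the baseline summaries of age and vaccination history (SAP 5) and in the check for "mis-stratification based on erroneous age or 2018-19 influenza vaccine history" (SAP 3.4.1). No primary or sensitivity analysis uses them, and no reason is given.

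**The concern.** Stratified randomisation balances the variation between strata across the arms, so that variation does not add to the sampling error of the treatment difference. An unstratified 2x2 interval still counts it in the standard error. If the strata predict seroconversion, the interval is too wide for the design, its true one-sided error falls below 2.5%, and some power is lost.

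The SCR is where this could matter. Non-inferiority must be shown on both endpoints for all four strains. SAP 9 puts GMT power at about 100% and SCR power at about 97.5% per strain, so the SCR sets the overall 90%. It is also the endpoint with no covariate adjustment at all.

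**Working it through.** **1. Planned sample size.** Inputs from SAP 9: SCR 0.50 and 0.48, margin 10 points, one-sided 0.025, about 97.5% power per strain, 10% attrition. The distance from the assumed difference to the margin is 0.10 − 0.02 = 0.08.

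- n = (1.96 + 1.96)² × (0.50×0.50 + 0.48×0.52) / 0.08² = 15.37 × 0.4996 / 0.0064 ≈ 1200 per group. With per-strain power 0.90^(1/4) = 0.974, n = 1190. The plan's figure lies between them: "Sample size was estimated to be 1195 in each group by assuming equal size in each group".
- At n = 1195, SE = √(0.4996/1195) = 0.02045. Per-strain power = Φ(0.08/0.02045 − 1.96) = 97.46%, and 0.9746⁴ = 90.2% over four independent strains.
- 1325 less 10% is about 1192 per group, giving 97.43% per strain and 90.1% overall.

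The plan's figure reproduces. The target is met without stratification, with almost nothing to spare under independence.

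**2. Approximate effect of stratifying.** Let R² be the share of seroconversion variance explained by the strata, and SE₀ the unstratified standard error. With balance within strata, the true standard error is SE₀√(1 − R²).

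- Unstratified power = Φ((0.08 − 1.96 SE₀) / (SE₀√(1 − R²)))
- Stratified power = Φ(0.08 / (SE₀√(1 − R²)) − 1.96)
- Unstratified one-sided error = 1 − Φ(1.96/√(1 − R²))

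At n = 1195, four-strain power goes from 90.4% to 90.6% for R² = 1%, from 90.6% to 91.1% for 2%, from 91.3% to 92.3% for 5%, and from 92.3% to 94.1% for 10%. Unstratified error falls from 2.50% at R² = 0 to 1.94% at R² = 10%.

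**3. The actual intervals.** The documents give no stratum-specific SCRs or stratum sizes, so these are assumptions: 1192 per arm, four equal age-by-vaccination strata of 298 with exact balance, control SCR averaging 0.50, and additive SCR gaps between the age groups and between the vaccination groups. R² is the variance of the stratum SCRs divided by 0.25. For example, gaps 10/10 give SCRs of 0.60, 0.50, 0.50 and 0.40, so R² = [(0.10² + 0 + 0 + 0.10²)/4]/0.25 = 2%.

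The planned Newcombe interval was evaluated by exact enumeration. The stratified Newcombe interval (Mantel-Haenszel weights) was evaluated on 2,000,000 simulated trials per scenario and true difference. Error is at a true difference of −10 points, power at −2 points.

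| Gaps, age/vaccination (points) | R² | Half-width, planned → stratified (points) | Error of planned interval | Four-strain power, planned → stratified |
|---|---|---|---|---|
| 0/0 | 0% | 4.00 → 4.00 | 2.48% | 90.2% → 90.2% |
| 10/0 | 1% | 4.00 → 3.98 | 2.43% | 90.4% → 90.9% |
| 10/10 | 2% | 4.00 → 3.96 | 2.37% | 90.7% → 91.5% |
| 10/20 | 5% | 4.00 → 3.90 | 2.19% | 91.3% → 92.4% |
| 20/25 | 10% | 4.00 → 3.79 | 1.90% | 92.4% → 94.3% |

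The stratified interval's own one-sided error is 2.5% to 2.6%. Unequal strata (15/50/10/25%) give gains of 0 to 1.6 points. With correlation 0.6 between the strain statistics, the largest gain falls from 1.9 to about 1.4 points.

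**4. GMT.** At a true ratio of 1.0, SD 0.4 (the upper value in SAP 9) and 1192 per arm, the expected lower bound is 10^(−1.96 × 0.4 × √(2/1192)) = 0.929. If the strata explained a further 10% of variance, multiplying the SD by √0.90 gives 0.932. The margin is 0.67, so stratum terms make no practical difference.

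**The case against.** The strongest reply is that nothing here is broken. An unstratified, slightly conservative analysis that meets its power target is a legitimate choice, and the documents state the purpose of stratification as balance, which the randomisation delivers. Several points follow.

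- **The gain appears where it is least needed.** If the strata explain nothing, power is 90.2% either way. If they explain 5% or 10%, the planned analysis has already risen to 91.3% or 92.4%. This is correct.
- **Planned power may be understated.** With correlation 0.6 between strains, the unstratified plan gives 92.7% at 1195 per arm. With SCRs of 0.40 against 0.38 it gives 92.2% under independence. These figures weaken the argument that there is no reserve.
- **Part of the gain is extra type I error.** With gaps 10/0, a separate simulation puts the stratified interval's error at 2.61%, against 2.43% for the planned one. The step 2 approximation, which holds error at 2.5%, gives a gain of 0.2 points there rather than 0.5.
- **The top of the range is demanding.** R² = 10% needs gaps of 20 and 25 points together. If a quarter of subjects were unvaccinated, with SCR 0.65 against 0.45 in the rest, vaccination history alone would explain 3%.
- **The remedy is partial and has a cost.** It leaves out site, one of the three factors, and it changes a primary estimator already written into the protocol.

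All of this limits the size and urgency of the point. It does not explain why factors chosen as worth balancing are absent from every analysis, including sensitivity analyses, of the endpoint that limits power.

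**Conclusion.** The concern holds as an efficiency and consistency point, not a validity defect. Neither primary analysis uses the stratification factors. To the extent that they predict seroconversion, the planned SCR interval is conservative, so the omission cannot create a false non-inferiority claim. For 0% to 10% of variance explained by age group and prior vaccination, four-strain power would rise by 0 to about 1.9 points under independence.

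That range rests on assumed stratum SCRs and sizes and on exact within-stratum balance, so it says nothing about imbalance after per-protocol exclusions. At the low end, part of the gain reflects the stratified interval's slightly higher error. The GMT half matters only for consistency. The change is worth making but not essential.

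**What to change.** Settle this before the Day 28 unblinding, in SAP 7.1.1 and 12.2, with protocol 10.4.1.1 brought into line:

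1. Make the primary SCR interval a stratified Newcombe interval with Mantel-Haenszel weights over the four strata formed by age group and 2018-19 vaccination.
2. Add age group and 2018-19 vaccination as fixed factors to the GMT ANCOVA, alongside log10 Day 0 titer.
3. Leave site out of both and say why: the number of sites is not given, and site-level cells may be sparse.
4. Use the strata as recorded in the IWRS at randomisation, since SAP 3.4.1 provides for mis-stratification.
5. Keep the unstratified analyses as sensitivity tables.

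Margins and decision rules do not change. The cost is a few lines of SAS, some SAP wording and at most three degrees of freedom, with no new data or subjects. The larger item is procedural: under protocol 9.5, changing 10.4.1.1 needs a signed amendment and IRB submission. If the sponsor finds that disproportionate, the minimum is a pre-specified stratified sensitivity analysis in the SAP, or a sentence saying why the strata are omitted.

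### The SAP's sample code reads one level of the seroconversion flag for the per-arm SCR and the other for the SCR difference; with a 0/1 flag the per-arm rates would be those of non-seroconverters

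*SAP*

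**What the plan says.** SAP 7.1.1 gives sample code for the primary SCR difference. It starts "proc freq data = fludata noprint" and then has "tables trt*seroconvind / riskdiff (column=2 cl=(newcombe", so it explicitly selects the second column of `seroconvind`.

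SAP 7.2 defines the rate in words: "Seroconversion rate (SCR) defined as proportion of subjects in a given treatment group" who meet the seroconversion criterion. It then says the rate and interval are calculated "using the Clopper-Pearson method with the following sample SAS code". That code runs on the same dataset name, by treatment, and contains "tables seroconvind / binomial(exact) alpha=.05". It names no level.

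For seroprotection SAP 7.2 prints no code and says only "SPR and corresponding 2-sided exact binomial 95% CIs will be constructed similarly using the Clopper-Pearson method". It also states that microneutralization (MN) results, including SCR, use the HAI methods.

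Neither fragment sets an ordering option or a format. The SAP does not give the coding of `seroconvind` or the order of `trt`. SAP 2.2.1 defines the contrast as Quad-NIV minus Fluzone, with a lower confidence bound of at least -10% required.

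**The concern.** The two fragments use the same two-level flag. One names level 2. The other names none, and PROC FREQ then takes level 1. Under any single coding, one fragment describes responders and the other non-responders, while the SAP text defines SCR only for responders.

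SCR and SPR are secondary endpoints, and the SCR difference is half of the primary decision rule. SAP 10 allows the Day 28 unblinded results to go to regulators in an abbreviated report, so the first tables matter. At rates near 50% a complemented rate does not look odd by itself. The per-arm fragment also suppresses printed output, so a programmer would not see the heading that shows which level was estimated.

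**Working it through.** **Inputs**
- Planning rates (SAP 9): "the SCR of reference group (Fluzone Quadrivalent) is assumed to be 0.5 and the SCR of treatment group (Quad-NIV) is assumed to be 0.48".
- Margin (SAP 9): "demonstrate a non-inferiority margin for SCR difference of -10"%. One-sided level 0.025; 1195 evaluable per group.
- Software behaviour, assumed because the documents do not state it and SAS was not run: `binomial` without a level takes the first ordered level, and `riskdiff` subtracts row 2 from row 1.

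**The plan's own figure.** Unpooled normal formula: n = (z_α + z_β)² × [p₁(1-p₁) + p₂(1-p₂)] / (margin - expected loss)².
- 97.5% power: (1.960 + 1.960)² × (0.2500 + 0.2496) / 0.08² gives 1200.
- Power 0.9^(1/4) = 0.974 per strain: 1190.
- The SAP states 1195. At 1195 the power is 97.46% per strain, and 0.9746⁴ = 90.2% overall. The planning figures reproduce and are not in dispute.

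**What each fragment returns.** Write Q and F for the true SCRs (Quad-NIV 48%, Fluzone 50%; correct difference -2).

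| Flag order | Row 1 | Per-arm output (level 1) | Difference (column 2, row 1 - row 2) |
|---|---|---|---|
| Non-responder first (0/1, N/Y) | Quad-NIV | 1-Q, 1-F = 52, 50: wrong | Q-F = -2: right |
| Non-responder first | Fluzone | 52, 50: wrong | F-Q = +2: sign reversed |
| Responder first (1=yes, 2=no) | Quad-NIV | Q, F = 48, 50: right | (1-Q)-(1-F) = F-Q = +2: sign reversed |
| Responder first | Fluzone | 48, 50: right | (1-F)-(1-Q) = Q-F = -2: right |

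In the last row the two reversals cancel.

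**Size with intervals, n = 1195 per arm.** 0.48 × 1195 rounds to 574 seroconverters on Quad-NIV, and 1195 - 574 = 621 are non-seroconverters. The Clopper-Pearson limits are the 0.025 quantile of Beta(x, n-x+1) and the 0.975 quantile of Beta(x+1, n-x).
- Correct level: 48.0% (45.2 to 50.9).
- First level of a 0/1 flag: 52.0% (49.1 to 54.8).

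The Newcombe limits combine the Wilson limits (l, u) of each arm: d - √[(p₁-l₁)² + (u₂-p₂)²] and d + √[(u₁-p₁)² + (p₂-l₂)²].
- Correct: -2.0% (-6.0 to 2.0), which meets the margin.
- Sign-reversed arrangements: +2.0% (-2.0 to 6.0).

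**Illustration for the sign-reversed arrangements only** (rates chosen here, not taken from the documents)
- 38% versus 50%: correct -12.1% (-16.0 to -8.1), fails; reversed +12.1% (8.1 to 16.0), passes.
- 60% versus 50%: correct +10.0% (6.0 to 13.9), passes; reversed -10.0% (-13.9 to -6.0), fails.

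**Would comparing rates with the difference catch it?** Set the tabulated Quad-NIV minus Fluzone rates against the `riskdiff` estimate. Rows 1 and 3 of the table disagree (+2 against -2, and -2 against +2) and are caught. Row 2 agrees (+2 and +2) although both are wrong. That check is therefore not enough alone.

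**The case against.** The strongest reply is that both fragments are labelled sample code and the text governs. SCR, SPR and the direction of the contrast are all defined in words, so no analysis choice is left open. The code is visibly schematic: the arm variable is `trt` in one fragment and `Treatment` in the other, and the difference fragment suppresses output without saving any. SAP Table 6 lists rates and differences among the reported results, so 52% and 50% beside a difference of -2% would conflict on sight. This stands as a limit on weight: the point is a specification defect, not evidence that any result would be wrong. It does not remove the contradiction, because the two fragments cannot both implement the definition by reading the responder level.

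A reader might infer that the primary non-inferiority decision is inverted as written. The documents do not support that. The flag coding is not given, and choosing `column=2` is most naturally read as picking the responders of a 0/1 flag. SAP Table 1 labels Quad-NIV as group A and Fluzone as group B; if `trt` carries those labels, Quad-NIV sorts first. Under that pair of assumptions the primary difference is correct. Reversal needs one, and only one, of the two orderings to be the other way; sorting by vaccine name, for example, would put Fluzone first.

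A reader might also infer that SPR is definitely affected. No SPR code is printed. The SAP's wording carries over an interval method and does not itself select a level, so the exposure is conditional on copying the SCR code.

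**Conclusion.** The mismatch is real and does not depend on how the flag is coded. With a 0/1 flag, the per-arm SCR and its Clopper-Pearson interval would be for non-seroconverters: 52% versus 50% at the planning values instead of 48% versus 50%. SPR and MN SCR would share this if programmed the same way. The primary difference keeps its correct sign in two of the four arrangements and reverses in the other two: responders first with Quad-NIV in row 1, or responders second with Fluzone in row 1.

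This rests on the standard PROC FREQ defaults, and the 0/1 coding is an assumption. A complemented rate has the same interval width and can be restored from the same data. It is a cheap correction that should be made before the Day 28 programming is released.

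**What to change.** In SAP 7.1.1 and 7.2:

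1. State that `seroconvind` and the SPR flag are coded 0/1 with 1 = responder.
2. Write `binomial(exact level='1')` for SCR and SPR, and for MN SCR if the code is reused.
3. Keep `column=2` for the difference, and fix the order of `trt` so that row 1 is Quad-NIV.
4. Add two checks: the tabulated Quad-NIV minus Fluzone rates equal the `riskdiff` estimate, including sign; and the responder counts agree with an independent count from the titers under the SAP definition.

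Writing `level=2` without stating the coding would not be safe. With 1 = yes, 2 = no and Quad-NIV in row 1, both fragments would then read non-responders, and the first check would still pass (+2 and +2). That is why the coding and the count check are both needed.

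The cost is one code option, two sentences on coding and row order, and two programming checks. No sample-size figure, estimand or interval method changes.
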